9.2 SAMPLE SIZE DETERMINATION

We hypothesize that EPP IUD expulsion will be non-inferior to interval insertion. We propose that greater than or equal to a 6% difference in expulsion at 6 months postpartum between the two arms is clinically meaningful (6% non-inferiority margin). Therefore, we estimate that 404 women will be needed [202 in each arm] to achieve an 80% power to detect a difference of 6% in expulsion at 6 months at a significance level of .05 (two-sided alpha), assuming a 15% loss to follow up and that 5% of IUDs would not be placed after randomization (due to patient preference or new medical contraindication or inability to place the IUDs) and assuming a 4% expulsion rate in the interval group. We estimate that enrolling 404 patients allows us to achieve an 80% power to detect a difference of 6% or more between groups with a 1-sided type 1 error of 0.25%.

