9.3 POPULATIONS FOR ANALYSES

The following datasets will be utilized for analysis:

- Intention-to-Treat Analysis Dataset: All participants randomized with known outcomes at the 6 month follow up visit*.
- Modified Intention-to-Treat Analysis Dataset: Participants who received an IUD within 6 months of delivery with known outcomes at the 6 month follow up visit*.
- Per-Protocol Analysis Dataset: Participants who received an IUD within the specified timeframe as designated by their group assignment with known outcomes at the 6 month follow up visit (14-28 days in the early group and 42-56 days in the interval group)*.

*participants known to have an IUD outcome by ultrasonography, pelvic examination, or a contact up to 240 days postpartum will be included.

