9.4.3 ANALYSIS OF THE SECONDARY ENDPOINT(S)

Partial IUD expulsion and perforation will be analyzed with the same methods as the primary outcome. IUD discontinuation over the six-month study period will also be analyzed using survival analysis. Data will be censored either (1) at the last date of contact if a participant is lost to follow up or (2) time of IUD removal. The Log-rank test will be used for an unadjusted comparison of the two survival functions. This will be presented graphically using Kaplan-Meier curves.

For other secondary outcomes, normally distributed, continuous variables will be compared using Student's t-tests as appropriate. The Mann-Whitney U test will be used to compare other continuous variables that are not normally distributed. Proportions will be compared using chi-square tests. For small cell sizes, Fisher's exact test will be used as appropriate.

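### The discontinuation survival analysis has a censoring rule for women lost to follow-up, but no stated analysis set clearly contains them

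*Combined protocol and SAP*

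**What the plan says.** Section 9.4.3: "IUD discontinuation over the six-month study period will also be analyzed using survival analysis". Two censoring times are given: "at the last date of contact if a participant is lost to follow up", and "time of IUD removal". The arms are compared by log-rank test and shown as Kaplan-Meier curves. No analysis population is named for this endpoint.

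Section 9.3 lists the datasets on which analyses will be run:

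- Intention-to-treat: "All participants randomized with known outcomes at the 6 month follow up visit".
- Modified intention-to-treat (MITT): "Participants who received an IUD within 6 months of delivery with known outcomes at the 6 month follow up visit".
- Per-protocol: "Participants who received an IUD within the specified timeframe as designated by their group assignment with known outcomes at the 6 month follow up visit".

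A footnote to all three adds that "participants known to have an IUD outcome by ultrasonography, pelvic examination, or a contact up to 240 days postpartum will be included". It sets a latest date but no earliest one.

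Section 9.4.2 also removes from the MITT analysis women who leave the study at any time after randomisation. Section 9.2 sizes the trial "assuming a 15% loss to follow up" and 5% non-placement.

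**The concern.** A censoring rule for lost women presupposes that they are in the risk set until they are lost. Section 9.3 admits only women whose 6-month outcome is known, and a woman lost at month 3 with her IUD in place normally has no such outcome. Applied as written, the datasets take out the women the censoring rule was written for. In the MITT set, withdrawals go the same way under 9.4.2.

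The damage depends on who else is removed. An expulsion or removal recorded at month 3 arguably settles the IUD outcome, whereas an IUD still in place at month 3 does not. If the first woman is kept and the second deleted, membership of the set depends on the outcome, and Kaplan-Meier estimates are biased upward even when loss is non-informative. Two analysts could build different datasets from the same text and draw different curves.

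**Working it through.** **Inputs.** From 9.2: N = 404 (202 per arm), 15% loss, 5% of IUDs not placed. The documents give no discontinuation rate, no loss by arm and no share of discontinuations that are removals, so those values below are assumptions.

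**The plan's own figure.** The plan gives no number for discontinuation. Its N does reproduce: (1.960 + 0.842)² × 2 × 0.04 × 0.96 / 0.06² = 167.4, so 168 per arm. Then 168 × 1.20 = 201.6, so 202 per arm and 404 in total.

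**Women affected.** Expected IUD recipients: 404 × 0.95 = 383.8, about 384. Lost: 383.8 × 0.15 = 57.6, about 58. Those who discontinued before being lost would stay in the set, so the number deleted is somewhat lower (see the table).

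**Case A: event-free lost women deleted, lost women with a recorded discontinuation kept.** Let d be true 6-month discontinuation and l the loss, both with constant hazards and independent. The probability of discontinuing before loss is

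E = [ln(1−d) / (ln(1−d) + ln(1−l))] × [1 − (1−d)(1−l)].

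No one in the retained set is censored before 6 months, so, counting every discontinuation as an event, Kaplan-Meier reduces to a proportion: E / [E + (1−d)(1−l)].

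At l = 15%:

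| True d | E | (1−d)(1−l) | Estimate | Error (points) | Deleted, of 384 |
|---|---|---|---|---|---|
| 10% | 0.0924 | 0.7650 | 10.8% | +0.8 | 55 |
| 15% | 0.1388 | 0.7225 | 16.1% | +1.1 | 53 |
| 20% | 0.1852 | 0.6800 | 21.4% | +1.4 | 52 |

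The result depends somewhat on when loss occurs. At true 10% and 15% loss, simulation with loss spread evenly over the period gives 10.7%. Placing all loss very early gives 10.2%, and very late 11.5%.

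**Unequal loss under Case A.** With true 15% in both arms, 10% loss gives 0.1426 / 0.9076 = 15.7% and 20% loss gives 0.1348 / 0.8148 = 16.5%. Before rounding the gap is 0.84 points. With 192 recipients per arm, the standard error of a difference is about √(2 × 0.15 × 0.85 / 192) = 3.6 points.

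**Case B: all lost women deleted, whatever is known about them.** With independent loss the estimate is d(1−l) / (1−l) = d. Simulation at 15% loss returns 5.0, 9.9, 20.0 and 30.0% for true 5, 10, 20 and 30%. If lost women discontinue more often than others, this rule understates discontinuation.

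**Case C: lost women kept and censored at last contact, removal counted as an event.** Simulation returns the same 5.0, 9.9, 20.0 and 30.0%.

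**Removal censored, as 9.4.3 is worded.** If a constant share s of discontinuations are removals and these are censored, the Case A estimate at true 10% becomes 1 − (1 − 0.1078)^(1−s). That is 5.5% at s = 50% and 2.3% at s = 80%. These downward errors of 4.5 and 7.7 points exceed the +0.8.

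**The case against.** The strongest reply is that 9.4.3 assigns none of the 9.3 datasets to the discontinuation analysis. Section 9.4.2 ties MITT and per-protocol to the primary outcome, and 9.4.3 carries those methods over only to partial expulsion and perforation. The discontinuation analysis has its own rule, which makes sense only if lost women are included, so the specific rule should override the general list. The footnote also has no earliest date and can be read as admitting a woman whose IUD status is known from an earlier contact. This stands in part: deletion is the literal reading, not the only one. But 9.3 presents its datasets as those used for analysis, no other is defined, and if the footnote admits any earlier contact the 6-month condition means little. The two rules still need reconciling.

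A reader might infer that the plan overstates discontinuation, or that unequal loss will produce a false difference between arms. The documents support neither as a flat statement. Overstatement needs the asymmetric retention of Case A, which the text suggests but does not state; under Case B with independent loss it is zero. The illustrated gap between arms is about a quarter of one standard error, and the plan gives no reason to expect 10% v 20% loss. Removal censoring in the same sentence may reverse the sign altogether.

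**Conclusion.** The inconsistency is real: 9.4.3 has a censoring rule for lost women, 9.3 read literally excludes nearly all of them, and no other population is named. The consequence is conditional and modest. If event-free lost women are dropped while recorded discontinuations are kept, with 15% independent loss and constant hazards, the estimate is too high by about 0.8 points at an assumed true 10% and 1.1 points at an assumed true 15%. Follow-up from roughly 50 to 58 of about 384 recipients is also thrown away. The net direction of the analysis as worded cannot be settled from the documents: it depends on which lost women are kept, on whether removal is really meant to be censored, and on the share of discontinuations that are removals. This is a secondary endpoint, and neither the sample size nor the primary analysis changes.

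**What to change.** Add to 9.4.3: *The discontinuation analysis includes every woman who received an IUD, analysed in her randomised arm. The known-outcome condition of section 9.3 does not apply. Women who are lost or withdraw without a recorded discontinuation contribute time up to their last contact.* In the same edit, reconcile the removal wording so that IUD removal counts as a discontinuation event and not as a censoring time. Changing the population alone would leave the larger distortion in place.

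The cost is a short text change. Last-contact dates are already needed for the stated censoring rule. The one downside is an analysis set for this endpoint that differs from the primary set, which should be noted where the curves are reported. Censoring at last contact still assumes that loss is unrelated to discontinuation; the edit makes the analysis valid under that assumption but does not test it.

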1 PROTOCOL SUMMARY

1.1 SYNOPSIS

Title:	Early vs. Interval Postpartum IUD Insertion: A Multi-Site Randomized Controlled Non-Inferiority Trial
Study Description:	This is a randomized controlled non-inferiority trial comparing the expulsion rate of early postpartum IUDs (intrauterine devices) inserted between 2-4 weeks postpartum to the standard interval placement at 6-8 weeks postpartum
Objectives:	Primary Objective: Complete IUD expulsion at 6 months postpartum Secondary Objectives: Partial IUD expulsion at 6 months postpartum, IUD utilization, IUD removal, IUD perforation, pelvic infection, pain, vaginal bleeding, and user satisfaction at 6 months postpartum
Endpoints:	Primary Endpoint: Speculum and ultrasound evaluation Secondary Endpoints: Speculum, ultrasound and x-ray evaluation, self-reported outcomes (survey results)
Study Population:	Postpartum women who delivered an infant within the previous 10 days
Phase:	N/A
Description of Sites/Facilities Enrolling Participants:	Academic medical centers: the University of California, San Diego (UCSD); University of New Mexico (UNM); University of Illinois, Chicago (UIC); and Naval Medical Center, San Diego (NMCS)
Description of Study Intervention:	Postpartum insertion of IUDs at 2-4 weeks after delivery vs. 6-8 weeks after delivery
Study Duration:	2 years
Participant Duration:	6 months (with optional 12-month participation offered)

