3 OBJECTIVES AND ENDPOINTS

OBJECTIVES	ENDPOINTS	JUSTIFICATION FOR ENDPOINTS
Primary		
To determine if the risk of complete expulsion of EPP IUDs is non-inferior to interval PP IUDs	Diagnosis of IUD expulsion by speculum and ultrasound exam at 6 months postpartum. Expulsion defined as no IUD within the uterus by ultrasound or x-ray.	We propose that greater than or equal to a 6% difference in expulsion at 6 months postpartum between the two arms is clinically meaningful (6% non-inferiority margin).
Secondary		
To assess the proportion of participants utilizing the IUD at 6 months	Transvaginal and speculum exam to confirm presence of the IUD at 6 months.	From a public health perspective, the duration of IUD use is important for pregnancy prevention.
To determine if the risk of partial expulsion of EPP IUDs is non-inferior to interval PP IUDs	Diagnosis of IUD expulsion by speculum and ultrasound exam at 6 months postpartum. Partial expulsion defined as IUD protruding from the external cervical os on speculum exam or any part of the IUD seen below the internal cervical os on transvaginal ultrasound.	We propose that greater than or equal to a 6% difference in partial expulsion and perforation at 6 months postpartum between the two arms is clinically meaningful (6% non-inferiority margin).
Tertiary/Exploratory		
To assess the risk of perforation after EPP IUD compared to interval postpartum IUDs	IUD not visible in uterus on transvaginal ultrasound, but visible on pelvic x-ray at 6 months.	

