All women will be scheduled to have a routine postpartum visit with their designated prenatal care provider **between 42-56 days postpartum** according to the standard of care at the health centers. Women will be scheduled to see a nurse midwife or physician based on their obstetrical history and prenatal care. Women in the interval group will be assessed for IUD placement at this visit per the standard of care at the center. IUDs will be placed by the patient's usual prenatal provider or any provider that the patient would normally be referred to for IUD placement. Whether ultrasound guidance is used for placement will be at the discretion of the clinician. Participants will be compensated with a \$20 gift card for their time and participation. Participants will be asked to complete either the insertion visit questionnaire or the string check questionnaire depending on their assignment group. Providers will be compensated with a \$5 gift card for their time completing a brief questionnaire for every patient seen at six weeks postpartum.

D. Optional String Check Visit:

Whether a follow-up string check visit is scheduled after six weeks will be at the discretion of the clinician according to standard practice of the clinic. String checks are not recommended by the CDC but are common practice. If a string check is scheduled by the clinician at any time (according to their personal practice or participant needs) then the participant will be asked to complete the string check questionnaire at that time.

e. Six Month Follow Up Visit

All women will be scheduled for a 6-month follow up study visit to assess for IUD expulsion, perforation, pregnancy, IUD removals and acceptability. A study clinician will conduct a bimanual pelvic exam, a speculum exam, and a transvaginal ultrasound at this visit. Women will also be asked to complete the 6-month study questionnaire and will be compensated with a \$20 gift card for their time and participation. The clinician will attempt to stay blinded to the participant's group assignment by not reviewing the medical chart prior to the visit.

f. 12 Month Optional Follow Up Call

During baseline survey data collection, all women will be asked if they consent to a 12-month follow up phone call to assess for IUD expulsion, perforation, pregnancy, IUD removals and acceptability.

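### The survival analysis of IUD discontinuation censors women at IUD removal, so no removal can count as a discontinuation

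*Combined protocol and SAP*

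**What the plan says.** Section 9.4.3 names the endpoint: "IUD discontinuation over the six-month study period will also be analyzed using survival analysis". The next sentence gives two grounds for censoring: the last date of contact "if a participant is lost to follow up or (2) time of IUD removal". The comparison and display follow: "The Log-rank test will be used for an unadjusted comparison of the two survival functions", and "This will be presented graphically using Kaplan-Meier curves".

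No section defines the discontinuation event, counts removal as an event, or names a competing-risk method. Women still using the IUD at six months are not in the censoring list.

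Elsewhere, removal is treated as an outcome. The synopsis (Section 1.1) lists it among the secondary objectives: "Partial IUD expulsion at 6 months postpartum, IUD utilization, IUD removal, IUD perforation". Section 8.1 schedules a "6-month follow up study visit to assess for IUD expulsion, perforation, pregnancy, IUD removals and acceptability". Section 3 justifies the endpoint of IUD use at 6 months on the ground that "From a public health perspective, the duration of IUD use is important for pregnancy prevention".

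**The concern.** A woman stops using an IUD when it is removed or when it is expelled. In a time-to-discontinuation analysis both are events. Censoring is for women whose event time is unknown because observation stopped while they were still users.

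Coding a removal as censored tells the Kaplan-Meier estimator that the woman was a continuing user when last seen, with the same prospects as those who remain. Her removal produces no drop in the curve and adds nothing to the log-rank statistic. Removal is also unlikely to be independent of the outcome. If an IUD is taken out because it is causing trouble or sitting badly, even the expulsion-only curve that remains is open to bias.

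At stake is the only planned analysis that uses the timing of discontinuation. Its curves would show continuation well above the truth, and they could contradict the simple proportions with removal and with use at 6 months reported beside them.

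**Working it through.** The plan states no event count, power or expected rate for this analysis, so it has no figure of its own to reproduce.

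**Inputs from the documents (Section 9.2).** 202 women per arm; 15% lost to follow-up and 5% with no IUD placed; 4% expulsion in the interval arm.

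**Assumptions.** Expulsion is also 4% in the early arm. Removal risk *r* by 6 months is varied, because the documents give none; *r* and the expulsion risk *e* are each the risk if the other did not occur. Removal and expulsion times are independent and exponential over a common six-month window.

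**Women per arm.** Two values were used.
- 202 × (1 − 0.20) = 161.6, so 162.
- The evaluable number behind the plan's sample size, at one-sided 0.025 and 80% power: (1.960 + 0.842)² × 2 × 0.04 × 0.96 / 0.06² ≈ 167.4, so 168. Then 168 × 1.20 = 201.6, which gives the stated 202.

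**What each curve estimates at 6 months.**
- Removal or expulsion as the event: (1 − *r*)(1 − *e*), the true proportion still using.
- Removal censored, as written: 1 − *e* = 0.96, whatever the value of *r*.

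The overstatement is therefore *r*(1 − *e*):
- *r* = 5%: true 0.95 × 0.96 = 91.2%; shown 96%; overstated by 4.8 points.
- *r* = 10%: true 0.90 × 0.96 = 86.4%; shown 96%; overstated by 9.6 points.
- *r* = 15%: true 0.85 × 0.96 = 81.6%; shown 96%; overstated by 14.4 points.
- *r* = 20%: true 0.80 × 0.96 = 76.8%; shown 96%; overstated by 19.2 points.

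**Log-rank test, simulated (168 per arm, 1,000 trials per row, two-sided 5% level).**

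| Removal, arm 1 vs arm 2 | Mean removals per trial | Mean expulsions per trial | Rejects, removal as event | Rejects, removal censored |
|---|---|---|---|---|
| 5% vs 5% | 16.6 | 12.9 | 4.7% | 4.7% |
| 5% vs 10% | 24.8 | 13.0 | 32.0% | 4.6% |
| 5% vs 15% | 33.0 | 12.8 | 73.2% | 4.6% |
| 10% vs 20% | 49.3 | 12.4 | 61.4% | 3.4% |

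A separate simulation with 162 per arm (600 trials) at 10% vs 20% gave mean continuation of 0.865 vs 0.769 and 61% rejection with removal as the event. With removal censored it gave 0.960 vs 0.961 and 4.7% rejection.

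**Check by normal approximation (162 per arm, 86.4% vs 76.8%).** SE = √[(0.864 × 0.136 + 0.768 × 0.232)/162] = 0.0427. Then 0.096/0.0427 = 2.25, and Φ(2.25 − 1.96) ≈ 0.61, which agrees.

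**The case against.** The strongest reply is that the sentence is loosely worded. Saying that data are censored at removal may mean only that observation ends there, with removal still coded as the event. Or time to expulsion was meant, where stopping at removal is a familiar choice. Neither reading is supported anywhere in the documents. An analyst following the text would code removals as censored, and if expulsion was meant, the endpoint is misnamed. Either way the passage needs correcting.

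Several other points stand and limit the scope:
- Removals are not lost to the trial. Section 9.4.3 provides chi-square or Fisher tests for proportions, and use at 6 months is a separate endpoint that falls with each removal.
- The statement in Section 3 about duration of use supports that proportion endpoint, not the survival analysis directly.
- Censoring continuing users at six months can be inferred from the stated study period, so leaving it off the list is minor.
- The between-arm rates are illustrative. Section 9.1 predicts no difference in removals. If removals are equal, the log-rank test keeps its false-positive rate and only the height of the curves is wrong.
- The 4% expulsion rate in the early arm is an assumption; Section 2.2 reports no complete expulsions in three earlier studies of early placement.
- The simulations give both arms the same window. Taking 6 months as day 182, follow-up from insertion is 154 to 168 days in the early arm (insertion on days 14–28) and 126 to 140 days in the interval arm (days 42–56). Kaplan-Meier censoring accommodates this, but the time origin must be stated.

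**Conclusion.** The concern holds. Section 9.4.3 states a rule that gives the wrong result for the endpoint it names: applied as written, no removal enters the Kaplan-Meier estimate or the log-rank count. The direction does not depend on the assumed rates, since continuation is overstated whenever any removal occurs.

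The size does depend on them. For removal risks of 5% to 20% and 4% expulsion, the overstatement runs from about 5 to 19 percentage points. For the unequal removal rates tried, log-rank rejection is 32% to 73% with removals counted and 3% to 5% without. About 17 to 49 removals per trial are discarded as events, leaving about 12 to 13 expulsions.

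This is one secondary analysis. It should be corrected before the data are analysed, but it does not touch the primary non-inferiority comparison or the 404.

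**What to change.** Replace the censoring sentence in Section 9.4.3 so that it states:
- **Event:** the first of IUD removal or complete expulsion.
- **Censoring:** last contact for women lost to follow-up; the 6-month assessment for women still using the IUD.
- **Time origin and analysis set:** insertion is the natural origin, which restricts the analysis to women who received an IUD. Because the arms then have different lengths of follow-up, quote continuation at a time since insertion that both arms reach.

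If removal alone is of interest, add its cumulative incidence with expulsion as a competing event. If time to expulsion was what the authors meant, rename the endpoint and treat removal as a competing event.

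The cost is a sentence or two. Section 8.1 already has removals and expulsions assessed at the 6-month visit. The sponsor should confirm that their dates are recorded, and state how an expulsion first found at that visit is dated. No change to sample size or visits is needed.

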5.1 INCLUSION CRITERIA

In order to be eligible to participate in this study, an individual must meet all of the following criteria:

- 1) Gave birth less than or equal to 10 days ago
- 2) Desires to use an IUD for contraception (either copper or levonorgestrel-containing)
- 3) Willing and able to sign an informed consent
- 4) Willing to comply with the study protocol
- 5) Age greater than or equal to 18 years
- 6) English or Spanish speaking

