6.2 MEASURES TO MINIMIZE BIAS: RANDOMIZATION AND BLINDING

Participants will be randomized to receiving EPP or Interval IUD placement by chance with a computer-generated randomization scheme in alternating blocks of 4 and 6 stratified by IUD type and site. The group assignment will be in opaque sealed envelope that will be opened by the research assistant. The participant will not be blinded to the group assignment.

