9.4 STATISTICAL ANALYSES

9.4.1 GENERAL APPROACH

9.4.2 ANALYSIS OF THE PRIMARY EFFICACY ENDPOINT(S)

Our primary outcome, the proportion of women with complete IUD expulsion at 6 months after delivery in the two groups, will be compared in the modified intention-to-treat (MITT) cohort using the Wald test. Women who change their mind about receiving the IUD after randomization, choose to receive the IUD after 6 months, or women who choose not to participate in the study any time after randomization, will be excluded from analysis for the MITT analysis. In addition, we will present a per-protocol analysis. The per-protocol analysis will include women who received their treatment according to the timeframe in which they were randomized. For the early IUD insertion group, per-protocol analysis will include women with documented receipt of the IUD insertion between 14 and 28 days postpartum. For the interval IUD insertion group, the per-protocol analysis will include only women with documented receipt of a postpartum IUD between 42-56 days postpartum. In both the MITT and per-protocol analyses IUD expulsion rates will be compared using the 2-sided test of noninferiority. If the CI for the risk difference does not cross the prespecified 6% margin, noninferiority will be confirmed.

We will consider imputing missing data. However, if one group had no or few expulsion outcomes the model may not converge.

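### Randomisation is stratified by IUD type and site, but every comparison named in 9.4.2 and 9.4.3 is unstratified, which costs precision mainly on secondary outcomes that depend on device

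*Combined protocol and SAP*

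**What the plan says.** Section 5.1 admits women who meet the criterion "Desires to use an IUD for contraception (either copper or levonorgestrel-containing"), so two kinds of device are in the trial. Section 6.2 allocates by a "computer-generated randomization scheme in alternating blocks of 4 and 6 stratified by IUD type and site".

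The analysis sections then name these methods:

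- Primary outcome (9.4.2): complete expulsion "will be compared in the modified intention-to-treat (MITT) cohort using the Wald test", with the decision rule "If the CI for the risk difference does not cross the prespecified 6% margin, noninferiority will be confirmed".
- Partial expulsion and perforation (9.4.3): "Partial IUD expulsion and perforation will be analyzed with the same methods as the primary outcome".
- Discontinuation (9.4.3): "The Log-rank test will be used for an unadjusted comparison of the two survival functions".
- Other secondary outcomes (9.4.3): "Proportions will be compared using chi-square tests", with Fisher's exact test for small cells, and t-tests or Mann-Whitney for continuous variables.

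Neither IUD type nor site appears again anywhere in 9.4. Section 9.4.1, where a general rule on adjustment would normally sit, has a heading and no text in the document as supplied. Pain and vaginal bleeding are listed as secondary in the synopsis and have no analysis of their own, so they fall under the generic two-sample tests.

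**The concern.** Stratifying the allocation treats device and site as factors that may predict outcome. When such a factor does predict outcome, stratified allocation removes its contribution from the true variance of the arm difference, but an unstratified test still counts it. The reported standard error is then too large, the interval too wide and the test conservative.

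The stake is mainly in the secondary outcomes. Section 9.1 expects no significant difference in pelvic infection and similar satisfaction between arms. To the extent that device or site predicts those outcomes, an inflated standard error makes such findings easier to reach. Bleeding and pain could plausibly depend on whether the device releases a hormone, although no section says so and this is an assumption here.

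There is a smaller second issue. The MITT and per-protocol sets in 9.3 drop women after randomisation, so balance by device is no longer guaranteed in the sets actually analysed.

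**Working it through.** **Planning figure.** Inputs from 9.2: expulsion 4%, margin 6 points, two-sided alpha 0.05, power 80%, losses of 15% and 5%. With both arms at 4%:

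n = (1.96 + 0.8416)² × 2 × 0.04 × 0.96 / 0.06² = 167.4, so 168 per arm.

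168 × 1.20 = 201.6, so 202 per arm and 404 in total, which matches the plan. (The one-sided 0.25% also stated in 9.2 would need 285 per arm before losses. It does not reproduce 404 and is not used here.) Device type plays no part in this calculation. Evaluable women: 202 × 0.80 = 161.6 per arm. Expected expulsions: 161.6 × 0.04 = 6.5 per arm.

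**Variance removed by stratifying on device.** For copper share w, rates pC (copper) and pL (levonorgestrel), and overall rate p = w·pC + (1 − w)·pL, with the same rates in both arms:

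r = w(1 − w)(pC − pL)² / [p(1 − p)]

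The interval narrows by 1 − √(1 − r). The large-sample two-sided alpha of the unstratified test is 2Φ(−1.96/√(1 − r)).

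**Binary bleeding or pain outcome.** Shares and rates are assumed, including that copper has the higher rate.

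| w | pL / pC | r | Narrower CI | Actual alpha |
|---|---|---|---|---|
| 0.2 | 20% / 40% | 0.0064/0.1824 = 3.5% | 1.8% | 0.046 |
| 0.3 | 20% / 60% | 0.0336/0.2176 = 15.4% | 8.0% | 0.033 |
| 0.5 | 20% / 60% | 0.0400/0.2400 = 16.7% | 8.7% | 0.032 |

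**Complete expulsion.** Overall rate 4%, with assumed copper share 10-50% and assumed copper-to-levonorgestrel risk ratio 2 to 5.

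- Smallest gain (share 0.1, ratio 2; rates 7.27% and 3.64%): r = 0.3%.
- Largest gain (share 0.2, ratio 5; rates 11.1% and 2.2%): r = 0.00126/0.0384 = 3.3%.
- Middle case (share 0.2, rates 8% and 3%): r = 0.0004/0.0384 = 1.0%.
- 95% half-width at 161.6 per arm: 1.96 × √(2 × 0.0384/161.6) = 4.27 points unstratified; 4.27 × √(1 − 0.033) = 4.20 at best.
- Power: 78.6% unstratified, 78.7% to 79.9% stratified, a gain of at most 1.3 points.

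A simulation compared pooled and device-stratified Wald intervals (40,000 trials per scenario, 162 per arm, copper share 20-30%). Power differed by at most 0.4 points and one-sided type I error by at most 0.1 points. Both intervals had simulated one-sided error of about 3.1-3.5% at the margin, so the large-sample conservatism does not show for an outcome this rare, and stratifying neither helps nor harms there.

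**Device imbalance in the analysed sets.** The shift in the arm difference is the difference in copper share times the difference in rates.

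- If all of the 5% of IUDs not placed were copper users in one arm, a 20% share there becomes 15/95 = 15.8%. With rates of 8% and 3% the shift is 4.2% × 5 points = 0.2 points.
- A 10-point difference in share (assumed) gives 10% × 5 points = 0.5 points for expulsion, and 10% × 40 points = 4 points for an outcome at 20% versus 60%.

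**The case against.** The strongest reply is that an unadjusted comparison is a legitimate choice and nothing is invalid. With 1:1 allocation balanced by device the pooled comparison is unbiased, and the plan openly calls its log-rank comparison unadjusted. That stands. That the devices are pooled is also inferred from the named methods; no sentence says so.

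It is equally fair that the size rests on assumption. Bleeding and pain appear only in the synopsis, not in the objectives table or in 9.1, and have no scale or binary definition. The 3.5-17% therefore illustrates one form those outcomes might take.

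Three stronger readings are tempting and are not supported:

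- A reader might infer that the primary conclusion is at risk. The expulsion figures show that it is not.
- A reader might infer that losses after randomisation could produce a false timing effect on expulsion through device mix. That needs drop-out to depend on both device and arm, which nothing in the documents suggests, and the shift is about 0.2-0.5 points against a 6-point margin. The per-protocol set could lose more women, but the documents give no figure.
- A reader might infer that results by device are needed because counselling will be device-specific. Section 2.2 speaks of counselling on early insertion in general.

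**Conclusion.** The mismatch between design and analysis is real: two stratification factors are used at randomisation and neither enters a named comparison. The consequence is lost precision, not bias. It amounts to about 3.5-17% of the variance for a binary bleeding or pain outcome under the assumed device mix and rates, and 0.3-3.3% for complete expulsion. The non-inferiority conclusion is unlikely to change. Site is ignored in the same way, but the documents give nothing from which to size its effect. The change is worth making because the strata are already recorded, not because the planned tests are invalid.

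**What to change.** In 9.4.3, analyse the secondary outcomes by the randomisation strata: IUD type and site, collapsing site where events are sparse. Define IUD type as the device declared at randomisation. The MITT set requires only that some IUD was received, so stratifying on the device inserted would condition on a post-randomisation event. Specifically:

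- proportions now assigned to chi-square: Cochran-Mantel-Haenszel;
- normally distributed continuous outcomes: a linear model with arm and the strata;
- other continuous outcomes: the van Elteren test;
- discontinuation: a stratified log-rank test.

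In 9.4.2, report a Mantel-Haenszel risk difference stratified by IUD type, at least as a sensitivity analysis to the Wald interval. Carry it over to partial expulsion and perforation, which follow the primary method. Show arm-by-device counts descriptively for expulsion, bleeding and pain.

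The cost is SAP wording, with no added patients or procedures. The drawback is sparseness. Two devices at four sites make eight strata, and about 6-7 expulsions per arm leave fewer than two per stratum in total (13/8 = 1.6), so site must be collapsed for the primary outcome.
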